5.9.12 Mayo Partial IBD Score

The Mayo Partial IBD Score ([Appendix D](#)) is a non-invasive 9-point partial Mayo score used as an outcome measure for clinical trials assessing therapy for ulcerative colitis ([Lewis et al. 2008](#)). The partial score evaluates changes in stool frequency, rectal bleeding, and physician assessment of disease severity, with defined changes in the score correlating with clinical responses to treatment. The Mayo Partial IBD Score will be assessed by study-site personnel at all study visits in all subjects, including Screening and EOS.

The Mayo Partial IBD Score is to be administered pre-dose at Day 1 and Weeks 1, 2, 4, 8, 12, and 16 (End of Study) as outlined in the Schedule of Study Procedures ([Table 5.5-1](#)).

6 STUDY DRUG

6.1 CLINICAL SUPPLIES

[REDACTED]

[REDACTED]

6.2 STUDY DRUG ACCOUNTABILITY

The PI is responsible for ensuring that a current record of inventory/drug accountability is maintained. Inventory records must be readily available for inspection by the study monitor and are open to inspection by regulatory authorities at any time. Each shipment of drug supply for the study will contain a shipping manifest to assist the PI in maintaining current and accurate inventory records.

Upon receipt of the investigational drug, the designated site personnel will visually inspect the shipment, verify the number and condition of study drug received, and confirm receipt of study drug. Study-drug reconciliation will be performed based on the study-drug kits and the remaining returned syringes and compared to recorded results in the study-drug diary.

At the completion of the study, all unused study-drug supplies will be returned to the Sponsor (or designee) or disposed of by the clinic, per the Sponsor's (or designee's) written instructions.

6.3 STUDY DRUG STORAGE

At the clinical site, study drug is to be stored refrigerated at 2°C–8°C (36°F–46°F) in a secure, controlled-access location protected from light.

At the subject's home, study drug is to be stored refrigerated at 2°C–8°C (36°F–46°F) in a location protected from light (e.g., their refrigerator). Subjects will be instructed to take care in keeping study drug out of the reach of children and other family members who may have access to the storage location.

6.4 DOSE PREPARATION AND ADMINISTRATION

Subjects will be instructed to self-administer/dose at approximately the same time each morning over the 12-week treatment period. Study-drug syringes for SC injection should be

brought to room temperature prior to use. Study drug will be administered as a SC injection in the abdomen. On Day 1, subjects will be trained on self-administering a SC injection. On Weeks 1, 2, 4, 8, and 12, self-administration will occur in the clinic under observation by clinic staff. Re-training will be provided as required. Written preparation and study drug self-administration instructions will be provided to each subject. Subjects will be required to complete a daily study-drug administration diary.

6.5 REMOVAL OF STUDY BLIND

This will be a double-blind, placebo-controlled study. Breaking of the blind will be available to the PI through an [REDACTED]. The subject's treatment assignment will be available to the PI in the event of a medical emergency or an AE that necessitated identification of the study drug for the welfare of that subject. Except in the case of a medical emergency, the PI and clinic staff will remain blinded during the conduct of the study and until such time that all discrepancies in the clinical database are resolved (i.e., at the time of the database lock). The date and time when the PI removed the study blind for an individual subject will be documented by the [REDACTED] and an automated notification will be sent to the Sponsor. The contracted CRO's pharmacovigilance team may also be required to break the blind for regulatory reporting purposes.

7 ADVERSE EVENTS

7.1 DEFINITION AND GRADING OF SEVERITY OF ADVERSE EVENTS

An AE is defined as any untoward medical occurrence in a subject of clinical investigational participation administered a pharmaceutical product, whether or not considered drug related. A TEAE is an AE that is reported after administration of a dose of study drug.

AEs include the following:

- Unfavorable changes in general condition
- Subjective or objective signs/symptoms
- Concomitant diseases or accidents
- Clinically relevant adverse changes in laboratory parameters observed in a subject in the course of a clinical study

AEs comprise all disturbances of general health status, subjective and objective disease symptoms (including laboratory abnormalities), and accidents observed in the context of a clinical trial, irrespective of a possible causal relationship with the administration of the trial substance. Events occurring in the framework of a clinical trial during drug-free and post-treatment periods or under placebo are also to be designated as AEs.

All AEs, regardless of how identified (e.g., volunteered, elicited, noted on physical examination), will be recorded throughout the study (i.e., from time of consent until final Follow-up visit).

Subjects will be followed for resolution of AEs, by querying the subjects for an ongoing AE until resolved or until any unresolved AEs are judged by the PI to have stabilized or if lost to follow-up. Resolution of all AEs will be promptly documented by the clinic on the subject's eCRF.

Any pregnancy diagnosed during the study must be reported immediately to the PI and Sponsor, including pregnancy in female partners of male subjects. The pregnancy will be followed to term and/or outcome and this outcome must be reported to the Sponsor.

Pregnancy, in and of itself, is not regarded as an AE or SAE unless the birth results in a congenital anomaly/birth defect or there is suspicion that the study drug may have interfered with the effectiveness of a contraceptive medication or method.

Medication overdose may have occurred when an additional dose of a medication is known or suspected to have been taken (accidentally or intentionally) or when the dose administered exceeds the dose mandated by the protocol. An overdose can involve any study medication and should be reported whether or not there is an associated AE. An overdose is only considered an SAE if any of the defined criteria are met. Associated AEs should be recorded and assessed in the standard manner defined by the protocol. In cases of a discrepancy in drug accountability, an overdose will only be established when it is clear the subject has taken an extra dose or the investigator has reason to suspect additional doses were taken.

The PI will rate the severity of AEs using the CTCAE v4.03. Each CTCAE v4.03 term is a Medical Dictionary for Regulatory Activities (MedDRA) Lowest Level Term (LLT). The CTCAE displays Grades 1–5 with unique clinical descriptions of severity for each AE. Not all Grades are appropriate for all AEs. Therefore, some AEs are listed with fewer than five options for Grade selection. Grade 5 (Death) is not appropriate for some AEs and, therefore, is not an option.

7.2 CRITERIA FOR DETERMINING RELATIONSHIP TO DRUG

The PI will make a blinded determination of the relationship of the AE to the study drug (including placebo) using a four-category system (not related, possible, probable, definite) according to the following guidelines:

- **NOT RELATED** = an AE that does not follow a reasonable temporal sequence from administration of the drug and that can be reasonably explained by other factors, including underlying disease, complications, concomitant drugs, or concurrent treatment;
- **POSSIBLE** = an AE that follows a reasonable temporal sequence from the administration of the drug (including the course after withdrawal of the drug) and that cannot be excluded as being possibly caused by the drug (e.g., existence of similar

reports attributed to the drug and/or its analogues; reactions attributable to the pharmacological effect of the drug), although other factors such as underlying disease, complications, concomitant drugs, or concurrent treatment are presumable;

- **PROBABLE** = an AE that follows a reasonable temporal sequence from administration of the drug (including the course after withdrawal of the drug) and that can be excluded as being possibly caused by other factors, such as underlying disease, complications, concomitant drugs, or concurrent treatment.
- **DEFINITE** = an AE that follows a reasonable temporal sequence from administration of the drug (including the course after withdrawal of the drug), follows a known or hypothesized cause–effect relationship, and (if appropriate) satisfies the following:
 - Positive results obtained in drug sensitivity tests
 - Toxic level of the drug present in blood or other body fluids

7.3 REPORTING

An SAE is any untoward medical occurrence at any dose that results in any of the following outcomes:

- Death
- A life-threatening event (i.e., places the subject, in the view of the PI, at immediate risk of death)
- Inpatient hospitalization or prolongation of existing hospitalization
- A persistent or significant incapacity or substantial disruption of the ability to conduct normal life functions
- A congenital anomaly/birth defect
- Important medical events that may not result in death, be life-threatening, or require hospitalization may be considered SAEs when, based upon appropriate medical judgment, they may jeopardize the subject and may require medical or surgical intervention to prevent one of the outcomes listed in this definition.

An unexpected adverse drug event is any adverse drug event the specificity or severity of which is not consistent with the current IB or, if an IB is not required or available, the specificity or severity of which is not consistent with the risk information described in the general investigational plan or elsewhere in the current application.

An AE is associated with the use of the drug if a reasonable possibility exists that the event may have been caused by the drug.

SAEs that are unexpected and related are reportable to Regulatory Authorities. Reportable SAEs will be reported by the PI to the Sponsor and the responsible Institutional Review Board (IRB) or Ethics Committee (EC).

The Sponsor's assigned Safety Representative will be electronically notified via the Medidata system. The reporting in the system must be completed by study personnel within 24 hours of when an SAE is first recognized or reported. Written reports should only be used if the site has issues accessing Medidata. The Safety Representative will subsequently notify the Sponsor and the Sponsor's assigned Medical Monitor of all reported SAEs.

7.3.1 Serious Adverse Events Notification Requirements

Any SAE must be reported by the Investigator, immediately or within 24 hours of awareness of the event, through data entry in the Adverse Event eCRF via the Medidata Rave® electronic data capture system. If the Investigator does not become aware of the SAE immediately (e.g., study subject seeks initial treatment elsewhere), he/she is to report the event within 24 hours after learning of it and document the time he/she first learned of the SAE.

Immediate notification to NGM (via the contracted CRO's pharmacovigilance safety hotline telephone number) must occur if the SAE is fatal or life-threatening, irrespective of the extent of available AE information.

In the rare case the Medidata Rave system is not available, the paper Serious Adverse Event Report Form (SAERF) should be used and faxed to the contracted CRO's pharmacovigilance safety hotline fax number, according to the instructions provided in the study-specific regulatory binder. Once the Medidata Rave system is available the event details should be entered as soon as possible.

For all SAEs, the Investigator is obligated to pursue and provide detailed information to NGM in accordance with the timeframes for reporting specified above. In addition, the Investigator may be required to obtain additional follow-up information in an expedited fashion.

At the time of first notification, the Investigator or designee should provide the following information, if available.

- Protocol number
- Reporter (study site and investigator)
- Patient's study number
- Patient's date of birth
- Patient's gender
- Date of first dose of investigational product
- Date of last dose of investigational product, if applicable
- Action taken with investigational product
- Adverse Event term

- Time and date of occurrence of the event (start and stop dates if known)
- Severity
- Outcome
- A brief description of the event, outcome to date, and any actions taken
- The seriousness criteria (on) that were met
- Concomitant medication at onset of the event, if known
- Relevant past history information
- Relevant laboratory test findings
- Investigator's opinion of the relationship to investigational product. ("Is there a reasonable possibility that the investigational product caused the SAE? Yes or No?")

If requested by the contracted CRO's pharmacovigilance unit, any missing or additional relevant information concerning the SAE should be entered into the Medidata Rave system or faxed to the safety hotline fax number. The Investigator is required to comply with applicable regulations (including local laws and guidances) regarding the notification of his/her health authorities, IRB, principal and coordinating Investigators, study Investigators, and institutions.

NGM or its designee is responsible for submitting expedited safety reports to the appropriate regulatory agency for all confirmed suspected, unexpected serious adverse reactions (SUSARs). These reports will comply with the applicable regulatory requirements and with the International Conference on Harmonisation (ICH) Guideline for Clinical Safety Data Management: Definitions and Standards for Expedited Reporting (E2A). In the case of a fatal or life-threatening SUSAR, NGM or its designee will notify the appropriate regulatory agency as soon as possible but in no case later than 7 calendar days after NGM's initial receipt of the information. For a non-life-threatening SUSAR, the report will be submitted no later than 15 days after NGM is made aware of the event.

An SAE may qualify for expedited reporting to regulatory authorities if it is determined to be a SUSAR.

8 DATA ANALYSIS AND STATISTICAL CONSIDERATIONS

Details of statistical parameters and methods to be applied will be provided in a detailed Statistical Analysis Plan (SAP) prior to database lock (unblinding).

8.1 SAMPLE SIZE

A sample size of 20 subjects randomized per treatment group was chosen in light of logistical needs and so as to accumulate sufficient safety data on NGM282. The associated power to detect a treatment difference in the primary efficacy analysis, for either NGM282 comparison versus placebo, is at least 90%, based on the following assumptions:

A. ALP Population Mean Change from Baseline:

		NGM282 (either 1 mg or 3 mg)		Placebo
Subjects taking UDCA at Baseline		–75	0	
Subjects not taking UDCA at Baseline		–475	0	

UDCA = ursodeoxycholic acid.

B. Equal numbers of completing subjects for each of the four cells above
C. Population (not sample) standard deviation (SD) between subjects within each of the four cells above: 200
D. Analysis of variance with treatment, UDCA (yes/no), treatment with UDCA (all as classification variables), and baseline value (as a continuous covariate) in the model
E. 20% dropout rate, from randomization to Week 12, yielding 16 completing subjects per treatment group
F. Dunnett's 1-step adjustment for multiplicity, requiring a type 1 error rate of 0.027 (2-sided) for each comparison versus placebo

Assumptions underlying the means and SDs are based on studies evaluating UDCA as a first-line therapy and in studies where secondary or combination therapies with UDCA have been utilized. The power in the primary efficacy analysis may be slightly higher, since it incorporates Dunnett's step-down adjustment and utilizes repeated measures to reduce the power losses due to dropouts. On the other hand, power may decrease slightly, to the degree that unequal numbers of subjects are randomized taking and not taking UDCA. In addition, the probability that the observed least square (LS) mean treatment difference exceeds 30% of the placebo LS mean change has not been examined.

To randomize 60 subjects, approximately 90 will be screened.

If, in contrast, the population SD is 300, the power is roughly 81% for each NGM282 comparison versus placebo.

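### The power of roughly 81% at SD 300 does not follow from the listed assumptions, which give about 62% per comparison unless an unstated gain from the baseline covariate is assumed

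*Protocol*

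**What the plan says.** Protocol 8.1 lists six assumptions, A to F, and SAP 3.1 repeats them.

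- **A and B:** the mean ALP change on either NGM282 dose is -75 in the row "Subjects taking UDCA at Baseline" and -475 in the row "Subjects not taking UDCA at Baseline". It is 0 on placebo in both, and the cells have equal numbers of completers.
- **C:** the between-subject SD within each cell is 200.
- **D:** the model has treatment, UDCA, their interaction, "and baseline value (as a continuous covariate) in the model".
- **E:** 20% dropout, "yielding 16 completing subjects per treatment group".
- **F:** single-step Dunnett, "requiring a type 1 error rate of 0.027 (2-sided) for each comparison versus placebo".

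On these, power is put at 90% or more for either dose against placebo. The section adds that the primary analysis may do slightly better because it uses step-down Dunnett and "utilizes repeated measures to reduce the power losses due to dropouts". It ends: "If, in contrast, the population SD is 300, the power is roughly 81% for each NGM282 comparison versus placebo". Only the SD changes in that last sentence. It also says that the sample size "was chosen in light of logistical needs and so as to accumulate sufficient safety data on NGM282".

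**The concern.** Raising the SD from 200 to 300 cuts the standardised effect by a third. Under A to F, a design with about 94% power at SD 200 should then fall well below 81%. Either the figure came from inputs other than those listed, or an assumption that drives it was left out.

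This is the section's only sensitivity figure, so it carries the message about robustness to a larger SD. The protocol takes its means and SDs from studies of UDCA and of secondary or combination therapies with UDCA, so a larger SD is a realistic case. A reader of the current text would expect a miss rate of about 19% per dose; the listed inputs give about twice that.

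**Working it through.** **Inputs (Protocol 8.1, repeated in SAP 3.1)**

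- Difference averaged over equal UDCA strata: (75 + 475)/2 = 275.
- Completers per arm: 16, so 48 in three arms.
- Per-comparison alpha: 0.027, two-sided. Simulating the Dunnett critical value for three equal arms gives about 2.29, a per-comparison alpha of about 0.027, as stated.
- Error df: 48 minus 7 model parameters (six treatment-by-UDCA cells plus baseline) = 41. The two-sided 0.027 critical t is 2.294.
- Baseline correlation: none given. The first calculations treat the SD as residual (r = 0).

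**The plan's base case, SD 200**

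Noncentrality = 275/(200 × √(2/16)) = 275/70.71 = 3.889. Power from the noncentral t with 41 df is **94.1%**. The claim of at least 90% reproduces, which supports this reading of A to F.

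**The sensitivity case, SD 300**

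Noncentrality = 275/(300 × √(2/16)) = 275/106.07 = 2.593. Power is **61.9%** with 41 df. It is 60.4% with 27 df (two arms only) and about 65% by normal approximation. None is near 81%.

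**The two upward adjustments the plan names**

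Simulated power per dose with both doses effective, SD 300, r = 0, step-down Dunnett:

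| Effective n per arm | Power per dose |
|---|---|
| 16 (as assumed) | 67% |
| 18 (half the dropouts recovered) | 73% |
| 20 (all dropouts recovered) | 78% |

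Even full recovery of dropouts leaves the figure about 3 points short.

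**The baseline covariate**

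If 300 is the SD before adjustment, the residual SD is 300 × √(1 − r²), where r is the within-cell correlation of baseline with ALP change. Single-step test, 16 per arm:

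| Assumed r | Residual SD | Power at SD 300 |
|---|---|---|
| 0 | 300 | 62% |
| 0.3 | 286 | 66% |
| 0.4 | 275 | 70% |
| 0.5 | 260 | 76% |
| 0.58 | 244 | 81% |

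At r = 0.58, power at SD 200 would be 99%. That also satisfies a lower bound of 90%, so the base-case statement does not show which r, if any, was used.

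**What else would give 81%**

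With no covariate gain, single-step power is 79.8% with 23 completers per arm and 81.7% with 24. Both exceed the 20 randomized per arm.

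Several calculations that depart from A to F also land close:

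- 20 per arm at two-sided 0.05, ignoring dropout and Dunnett: 81.2%.
- 16 per arm at one-sided 0.05: 81.7%.
- 20 per arm at one-sided 0.027: 82.1%.
- The no-UDCA stratum alone, 8 per arm, difference 475: 80.5%.

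These show only that the origin of the figure cannot be recovered from the documents.

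**The case against.** The best counter-argument is that assumption D puts baseline in the model, and C reads naturally as an SD before adjustment. On that reading A to F give a range that depends on r, with 62% as its floor, and 81% lies inside the range. The planned primary analysis also combines the covariate with step-down testing and repeated measures. Simulating the three together at SD 300, 81% per dose is reached at about r = 0.51 with 16 per arm, r = 0.4 with 18 and r = 0.25 with 20. On this view the fault is an unstated assumption and not wrong arithmetic, and restating 62% could replace a figure that may be right.

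The numbers in this argument are correct, and the covariate route cannot be excluded. But no value of r appears in either document. Step-down and dropout recovery are offered there as possible extras beyond A to F, not as part of the stated figure. A reader who applies the listed inputs cannot obtain 81% under any version of the argument without supplying a number the plan omits. What does stand is that 62% must be labelled as assuming no covariate gain, and that stating the missing assumption is an equally good remedy.

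It is also fair to say that the practical effect is limited. The sample size was set on logistical and safety grounds, and no analysis or decision rule in either document uses the 81%.

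**Conclusion.** The concern holds. At SD 300, with a difference of 275, 16 completers per arm, two-sided 0.027 and no variance reduction from baseline, power is about 62% per comparison, or about 67% with step-down Dunnett. The stated 81% is therefore about 14 to 19 points too high at the stated number of completers, and about 3 points too high if step-down applies and every dropout is recovered. The chance of missing a true effect at a given dose is about 38% (33% with step-down). Step-down figures assume that both doses are effective.

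The stated figure can be right only with an extra assumption, such as a baseline correlation of about 0.58 for the single-step test. Whether that was intended cannot be told from the documents. The base-case power at SD 200 and the 0.027 alpha both check out. This should be corrected, but it does not undermine the design.

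**What to change.** In Protocol 8.1 and SAP 3.1, do one of the following.

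1. Restate the SD 300 power as roughly 62% per comparison (about 67% with step-down Dunnett), and say that this assumes no variance reduction from the baseline covariate.
2. Keep 81% and state what produces it, for example a baseline correlation of about 0.58. Say whether the SDs of 200 and 300 are before or after baseline adjustment.

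If the source calculation is on file, it will settle which applies. The cost is one sentence in each document, with either a less favourable sensitivity figure or one more declared assumption. Sample size, alpha, tests and enrolment stay as they are.
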